2.3.6 Venetoclax Drug Information Summary

See the Venetoclax Prescribing Label (Appendix) for additional details on nonclinical and clinical studies.

Bcl-2 overexpression has been implicated in maintaining the survival of AML cells and has been associated with resistance to chemotherapy and inferior overall survival ⁹⁵. Venetoclax (VEN) is a potent and selective small-molecule inhibitor of Bcl-2 that has demonstrated cell-killing activity against a variety of leukemia cell lines, primary patient samples and leukemia stem/progenitor cells ^{96,97}. VEN also has been found to synergize with agents known to down-regulate Mcl-1, including azacitidine. ⁹⁸

Based on the mechanism of action and nonclinical and clinical data available to date, the safety profile of venetoclax is well described. The most common adverse drug reactions across all indications are nausea, diarrhea, hematological effects, and serious and/or opportunistic infections. Hematologic effects include neutropenia/febrile neutropenia, thrombocytopenia, anemia, and lymphopenia. Upper respiratory tract infections are among the most common infections. TLS is an important identified risk and is predominantly seen in the CLL population with high tumor burden. Based on pre-clinical data, decreased spermatogenesis has been identified as a potential risk for venetoclax.

Summary of Venetoclax Nonclinical Pharmacology

Venetoclax is a potent, selective and orally bioavailable small molecule inhibitor of Bcl-2 that binds with > 1,000-fold higher affinity for Bcl-2 (dissociation constant $K_i < 0.010$ nM) than for Bcl-X_L (K_i - 48 nM or Mcl-1 ($K_i > 444$ nM).⁹⁶ In vitro, venetoclax has demonstrated cell killing activity against patient-derived chronic lymphocytic leukemia (CLL) cells and a variety of lymphoma and leukemia cell lines⁹⁶. Venetoclax has demonstrated potent killing of AML cell lines, primary patient samples, and leukemic stem/progenitor cells ex vivo, and has also exhibited anti-tumor efficacy in vivo, inhibiting the growth of AML cells systemically engrafted into immunocompromised mice.

Summary of Venetoclax Nonclinical Pharmacokinetics

The pharmacokinetics of venetoclax was evaluated in mice, rats, monkeys, and dogs. Venetoclax pharmacokinetic (PK) profile was characterized by low plasma clearance and low to moderate volumes of distribution. Half-lives ranged from 2.2 hours in monkeys to 12 hours in dogs.

Venetoclax demonstrated high protein binding to human, rat, dog, and monkey plasma proteins (> 99.9%). Blood to plasma ratios showed that venetoclax does not partition preferentially into the red blood cells. Following oral administration of venetoclax to nonclinical species and humans, parent compound and metabolites were mainly cleared via biliary excretion and fecal elimination, with minimal renal clearance.

Venetoclax is predominantly metabolized by cytochrome P450 (CYP) 3A4 (CYP3A4) in vitro; UDP-glucuronosyltransferases (UGTs) are not involved in the metabolism of venetoclax. In addition, venetoclax is also a substrate for P-gp and BCRP. Active uptake of venetoclax was not observed in cells overexpressing OATP1B1, OATP1B3 or OCT1. In vitro studies indicated that venetoclax is not an inhibitor or inducer of CYP1A2, CYP2B6, CYP2C19, CYP2D6, or CYP3A4 at clinically relevant concentrations. Venetoclax is a weak inhibitor of CYP2C8, CYP2C9, and UGT1A1 in vitro, but it is not predicted to cause clinically relevant inhibition due to high plasma protein binding. Venetoclax is a P-gp and BCRP inhibitor and weak OATP1B1 inhibitor in vitro. In vitro, venetoclax is metabolized by CYP3A4 and is a moderate inhibitor of CYP2C8. Definitive in vitro experiments showed that venetoclax is not predicted to be an inducer or inhibitor of the metabolism of CYP2C9 substrate compounds. Venetoclax is not a reversible inhibitor of CYP1A2, CYP2B6, CYP2D6, CYP2C19 or CYP3A4 ($IC_{50} > 30 \mu M$) in vitro and does not induce CYP3A4 or CYP1A2 at concentrations up to 10 μM .

Summary of Nonclinical Toxicology

Venetoclax has been assessed in repeated-dose general toxicology studies and in genetic, developmental/reproductive, and safety pharmacology studies. The primary toxicities associated with venetoclax administration included effects on the hematologic system (decreased lymphocytes and erythrocytes) in mice and dogs, the male dog reproductive system (testicular germ cell depletion), and embryo-fetal toxicity in mice.

Summary of Venetoclax Clinical Data

Clinical Efficacy Data for Venetoclax: Preliminary efficacy results are available for subjects with a variety of hematological neoplasms; the drug is approved for the treatment of CLL patients whose cells have a 17p chromosomal deletion. Preliminary data indicate that venetoclax shows promising efficacy in AML.

- In Study M14-212 the ORR for subjects treated with venetoclax monotherapy was 19%.⁹⁹
- In Study M14-358 the ORR for AML subjects (given venetoclax plus azacitidine or decitabine) was 68%.¹⁰⁰
- In Study M14-387 the ORR for AML subjects (given venetoclax plus low dose arac-C) was 75%.¹⁰¹

Venetoclax Clinical Pharmacology and Pharmacokinetics: Venetoclax clinical pharmacology is being evaluated in several Phase I to III clinical trials, and data are available from three Phase I studies (M12-175, M13-367, M12-630), four Phase Ib

studies (M13-365, M12-901, GO29440, GP28331), one Phase II study (M14-212) and five dedicated clinical pharmacology studies (Study M13-364, M14-497, M13-363, M14-253 and M15-101).

In the Phase 1 Study M14-358, preliminary pharmacokinetic results in 31 treatment-naïve AML subjects were available for venetoclax doses ranging from 400 mg to 800 mg when given in combination with decitabine (Arm A) or azacitidine (Arm B) and with or without posaconazole (Arm C). For Arm A and Arm B, venetoclax steady-state mean Cmax and AUC₂₄ (Cycle 2 Day 5) ranged from 1.77 – 3.36 µg/mL and 24.7 – 59.5 µg/mL, respectively. Based on the limited preliminary pharmacokinetic data, there was no evidence to suggest a marked effect of the co-administration of decitabine and azacitidine on the pharmacokinetics of venetoclax. In Arm C of this study, preliminary pharmacokinetic results from 6 subjects were available on Cycle 1 Day 20 (venetoclax 400 mg alone QD until Day 20) and Cycle 1 Day 28 (venetoclax 100 mg QD with posaconazole given from Day 21 to Day 28). Venetoclax Cmax and AUC following co-administration of venetoclax 100 mg with posaconazole were 2.1- and 2.7-fold higher respectively, compared to venetoclax 400 mg alone.

Preliminary pharmacokinetic results of venetoclax are available from 12 treatment-naïve subjects with AML in Cohorts 1 (600 mg) and 2 (800 mg) from the ongoing Phase 1 combination study of venetoclax and low dose cytarabine (Study M14-387). On Cycle 1 Day 10 (with cytarabine), venetoclax mean Cmax and AUC₂₄ values ranged from 2.25 – 2.56 µg/mL and 34.7 – 44.6 µg·hr/mL, respectively. On Cycle 1 Day 18 (venetoclax alone), mean Cmax and AUC values of venetoclax ranged from 2.38 – 2.89 µg/mL and 37.9 – 45.3 µg·hr /mL. Dose-normalized Cmax and AUC₂₄ of venetoclax on Cycle 1 Day 10 (with cytarabine) were comparable to dose normalized Cmax and AUC₂₄ on Cycle 1 Day 18 (venetoclax alone), suggesting that co-administration of cytarabine did not markedly affect venetoclax exposures.

Clinical Safety Data for Venetoclax: As of 05 June 2017, three Phase 1/2 studies have been conducted in the AML indication as described below.

Overview of Phase 2 Study M14-212: Venetoclax Monotherapy in AML

This is a completed study with single agent venetoclax in subjects with R/R AML and those unfit for intensive therapy. A total of 32 subjects were dosed. Exposure, safety, and efficacy data are available for this study.⁹⁹ The most common adverse events observed in ≥ 30% of the subjects in Study M14-212 were nausea (59.4%); diarrhea (56.3%); hypokalemia, vomiting (40.6% each); fatigue, headache (34.4% each); hypomagnesemia (37.5%); febrile neutropenia (31.3%); abdominal pain, cough, hypophosphatemia (28.1% each); epistaxis, hyperphosphatemia, hypocalcemia, malignant neoplasm progression (25.0% each); dyspnea, hypotension, peripheral edema, pyrexia, and pneumonia (21.9% each). Serious adverse events were reported in 27 subjects (84.4%), the most common being febrile neutropenia (28.1%), malignant neoplasm progression (25.0%), and pneumonia (15.6%). Three serious adverse events were considered to have a reasonable possibility of being related to venetoclax (i.e., 1 event each of diarrhea, febrile neutropenia, and pseudomonal bacteremia). No cases of TLS occurred during venetoclax treatment.

In this phase II multicenter trial single agent VEN produced an overall response in 5/32 relapsed/refractory AML patients (CR in 1 patient, CRI in 4 patients)¹⁰². Of the 5 patients with CR/CRI, 3 had *IDH* mutations suggesting that patients with *IDH* mutations may be

particularly sensitive to VEN.

Two ongoing trials are evaluating VEN combination regimens in treatment naïve patients with AML who are ≥65 years of age and who are not eligible for standard induction: (a) to evaluate the efficacy and tolerability of the combination of VEN with a methyltransferase inhibitor (azacytidine or decitabine) (ClinicalTrials.gov Identifier: NCT02203773); (b) to evaluate VEN with low-dose cytarabine (ClinicalTrials.gov Identifier: NCT02287233).

Overview of Ongoing Phase 1b Study (M14-358): Venetoclax in Combination with HMA in Treatment Naïve AML

As of 09 March 2016, a total of 45 subjects ≥ 65 years of age with treatment naïve AML ineligible to receive standard induction therapy were enrolled into the escalation stage at 3 dose levels of venetoclax at 400 mg, 800 mg, and 1200 mg. Venetoclax was administered daily during the 28-day cycles in combination with decitabine (20 mg/m² intravenously on Days 1 – 5 once every 28 days) or azacitidine (75 mg/m² intravenously or subcutaneously on Days 1 – 7 once every 28 days). Preliminary safety and efficacy data are available from the ongoing dose escalation stage of this trial.^{101,103}

The most common adverse events for all subjects in Study M14-358 were nausea (53.3%), diarrhea (44.4%), febrile neutropenia (40.0%), neutrophil count decreased (31.1%), platelet count decreased, cough, and fatigue (28.9% each), edema peripheral and hypokalemia (26.7% each). Events grade 3 and above were reported for the majority (91.1%) of subjects; the most common event was febrile neutropenia (40.0%). Serious adverse events were reported for 27 (60.0%) subjects, including febrile neutropenia (11 subjects), malignant neoplasm progression (3 subjects) atrial fibrillation, abdominal pain, non-cardiac chest pain, pyrexia, pneumonia, sepsis, bone pain (2 subjects each). All other events occurred in 1 subject each. The combination of venetoclax with decitabine and azacitidine demonstrates a tolerable safety profile.

As of 09 March 2016, the ORR, as assessed by the investigators for the subjects enrolled into the 3 dose levels, was 62.2% (28 of 45), with CR in 12 (26.7%), CRi in 15 (33.3%), and PR in 1 (2.2%). Four subjects (8.9%) were reported to have morphologic leukemia-free state (less than 5% blasts in bone marrow aspirate sample with at least 200 nucleated cells) after completion of Cycle 1. Eight patients (17.8%) had resistant disease. However, all of the patients with resistant disease had evidence of blast reduction at completion of Cycle 1. The patients enrolled into the 1200 mg dose level had a shorter follow-up at the time of this analysis.

The maximum tolerated dose has not been reached in either arm and dose escalation stage has completed enrollment. Enrollment into safety expansion at 400 mg and 800 mg dose of venetoclax in combination with both HMAs is ongoing.

Study M14-387: Study M14-387 titled, "A Phase 1/2 study of venetoclax in combination with low-dose cytarabine in treatment naïve subjects with acute myeloid leukemia who are ≥ 65 years of age and who are not eligible for standard anthracycline-based induction therapy," is an ongoing, open-label, multicenter safety and pharmacokinetics study. The primary objectives of the Phase 1 portion are to assess the safety profile, characterize pharmacokinetics, and determine the dose schedule, the MTD, and the RPTD of venetoclax in combination with low-dose cytarabine (LCD) in treatment-naïve AML subjects. The primary objectives of the Phase 2 portion of the study are to evaluate

preliminary estimates of efficacy (including ORR and TTP) and to characterize the toxicities of the combination at RPTD. Secondary objectives of the Phase 2 portion include evaluating leukemia response (rates of CR, CRI, PR, RD, and HR including transfusion support needs) and DOR. An additional exploratory objective includes the evaluation of biomarkers that may serve as surrogate or predictors for clinical outcomes for future studies.

Of the 25 subjects in Study M14-387, 24 (96.0%) experienced at least 1 treatment-emergent adverse event. The most common adverse events for all subjects in Study M14-387 were: nausea (54%), febrile neutropenia (41%), diarrhea (44%), decreased appetite (33%), and peripheral edema (31%). Adverse events leading to study drug discontinuation occurred in 4 (16.0%) subjects, including 1 event each of disease progression, acute hepatic failure, Candida pneumonia, and subdural hemorrhage. Fatal adverse events occurred in 5 (20.0%) subjects: 2 events of malignant neoplasm progression and 1 event each of acute hepatic failure, Candida pneumonia, and lung infection.¹⁰⁰

For further details of venetoclax preclinical studies, clinical studies, toxicities, pharmacokinetics, and adverse events please see the venetoclax Prescribing Label (attached).

2.4 RATIONALE FOR THE PROTOCOL

Evaluation of multiple costimulatory receptors from BM aspirates and peripheral blood in 75 AML patients (frontline and relapsed AML) as well as at baseline and every 4-8 weeks on our ongoing PD1/PD-L1 based clinical trials by 17-color flow-cytometry in the Leukemia Department in collaboration with the Immunotherapy Platform ([name] and [name]) at MDACC revealed that a number of checkpoint pathways beyond PD1/PDL1 play a role in AML, with our data supporting increased expression of OX40 and limited but identifiable expression of 4-1BB on CD4⁺Teffector phenotype, CD8⁺ phenotype, and CD4⁺ Treg phenotype T-cells in bone marrow aspirates of patients with AML¹⁵ (Williams P, et al ASH 2017 Oral presentation, abstract # 185): see updated data in section 2.6.1. These PD-1, PD-L1, OX40 expression data, the association between high PD-1/PD-L1 and poor outcome in AML, and the synergistic (often multifold improved) benefit seen with combined or sequential checkpoint blockade in multiple solid tumors supports our planned clinical trials of checkpoint blockade therapies in patients with AML. If appropriately identified, a percentage of AML and MDS patients may benefit from immunotherapy approaches targeting AML and MDS-specific immune checkpoints.

Preclinical data from PF-04518600 (OX40 mAb) suggest that it has limited efficacy as monotherapy but may have synergistic efficacy when combined with standard cytotoxic/radiation therapy or immunotherapy (e.g. OX40 + PD-L1).

Furthermore, the clinical exigency of AML requires that chemotherapy and/or targeted therapy must be used as well. Azacitidine is approved in the US and Europe for patients with MDS, and is approved in Europe and commonly used in the US to treat older patients with newly diagnosed AML. Hypomethylating agents (HMAs), azacitidine and decitabine, promote anti-tumor immune signaling by up regulation of interferon-gamma pathway genes, increased expression of HLA class 1 antigens, and activation of viral defense pathways.¹⁰⁶ The HMAs concurrently dampen anti-tumor immunity by increasing the expression of PD-1 and PD-L1 in solid tumors¹⁰⁷ and in myelodysplastic syndrome (MDS)/AML.¹⁰⁴ Up regulation of these immune checkpoint molecules may be a

mechanism of resistance to HMAs. Recent data shows that hypomethylating agents increase the expression of natural killer (NK)-cell activating receptors and enhanced antibody dependent cellular toxicity (ADCC) when administered in combination with a CD33-targeting ADCC inducing antibody¹⁰⁸. Furthermore, prior studies from MD Anderson and others have suggested that immune checkpoints such as PD-1, PD-L1, PD-L2 and CTLA-4 are upregulated by hypomethylating agent exposure.^{104,105} These preclinical data support the rationale for combination of anti-PD-L1 antibodies such as avelumab with hypomethylating agents such as azacitidine.

Following discussion and recommendations from the MDACC Department of Leukemia and Immunotherapy Platform, we propose a multi-arm study to evaluate checkpoint modulating therapies in combination with each other, and with epigenetic agents, antibody drug conjugates, and BCL-2 inhibitors in R/R AML. A combination of the glasdegib will additionally be tested in combination with an anti-CD33 monoclonal (GO) in relapsed AML.

This basket trial approach will enable the evaluation of safety, and pharmacodynamics activity of immune checkpoint modulating therapies in combination with each other, epigenetic agents, antibody drug conjugates, BCL-2 inhibitors, and other novel therapies in AML allowing rapid identification and expansion of promising arms and early closure of underperforming or excessively toxic arms. It will be of independent significance to achieve a better understanding of the tumor immunology of AML, how that is changed by immune checkpoint therapies and non-immune checkpoint therapies, and how both of these are related to clinical response, and to identify other checkpoint pathways and immune agonists that dominate the immune response in AML and develop predictive biomarkers for immunotherapies in AML. These goals will be achieved using a prespecified in-depth immune monitoring plan on bone marrow aspirate/biopsy and peripheral blood samples as specified in the correlates section portion of this protocol. The development and execution of such master trials will hopefully help accelerate the development, identification, and selection of the most active and tolerable combinations in AML.

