1.0 OBJECTIVES

1.1 Primary Objectives

1. To evaluate the safety of multiple combination regimens of IO-agents [PF04518600 (Ox40 agonist mAb), avelumab (PD-L1 antagonist mAb)], hypomethylator therapy (azacitidine), anti CD33 mAb (gemtuzumab ozogamycin, GO), Bcl-2 inhibitor (venetoclax) and smoothened pathway inhibitor (glasdegib) in patients with relapsed/refractory (RR) AML.

2. To evaluate the composite complete response (CRc) defined as CR + complete response with incomplete recovery of platelets (CRp) + complete response with incomplete recovery of counts (CRI) within 3 months of therapy initiation in patients with RR AML of:

Arm A. PF-04518600 alone,

Arm B. Azacitidine + venetoclax + GO

Arm C. Azacitidine + avelumab +GO

Arm D. Azacitidine + venetoclax + avelumab

Arm E. Azacitidine + avelumab + PF-04518600,

Arm F. GO + glasdegib

1.2 Secondary Objectives:

-To assess the morphologic leukemia free survival (MLFS), partial response (PR), hematologic improvement (HI) rate of patients with RR AML treated on arms A – F

-To assess relapse-free survival (RFS), time to next therapy (TNT), 4-week and 8-week mortality, and overall survival (OS) of patients with RR AML treated on arms A – F.

-To assess minimal residual disease (MRD) by multiparametric flow-cytometry at response (+/- 1 month) and assess correlation of MRD to OS in arms A – F.

1.3 Exploratory Objectives:

1. To study immunological and molecular features at baseline and at predefined time-points on-therapy with each combination in the peripheral blood and bone marrow to include: (a) quantification of immune ligand expression by the AML/MDS blasts and AML/MDS stromal components (MDSCs, monocytes and MSCs) including galectin 9, 4-1BBL, ICOSL, PD-L1, PD-L2, OX-40L, CD137L, others and (b) determination of the quantitative expression of positive and negative co-stimulatory molecules including 4-1BB, CTLA-4, ICOS, PD-1, OX40, LAG-3, TIM-3, HLA-DR, Ki67, others on T-lymphocyte subsets and (c) identification of the immunophenotype of tumor-infiltrating T-lymphocytes (TILs) pre- and post-therapy including CD8+, CD4+ effector, CD4+ regulatory TILs and central memory, effector memory, and naïve T-cell subsets among the CD4 and CD8 populations. These analysis will be done using multiparametric flow-cytometry (MFC) or multi-stain immunohistochemistry (IHC)

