2.5 Clinical experience with immune checkpoints in RR AML

We treated 53 patients on the azacitidine + PD1 inhibitor (nivolumab) for relapsed/refractory AML¹⁵ (see updated data from this trial submitted to ASH 2018, in section 2.6.2). N=35 patients were evaluable for response: N=6 (18%) achieved complete remission (CR)/ complete remission with insufficient recovery of counts (CRI) (3 CR, 3 CRI), N=5 (15%) had hematologic improvement (HI), N=9 (26%) had $\geq 50\%$ BM blast reduction, N=3 patients (9%) had stable disease > 6 months, and 12 (34%) had progression. The CR/CRI/HI (N=11) have been durable, with only one relapse in a patient who achieved CR/CRI/HI [CR duration; not reached (NR)]. The 4- and 8-week mortality were 0% and 6%, respectively. The median overall survival for the 35 evaluable patients was 9.3 months (range, 1.8 – 14.3) (Fig 1), and this compares favorably to historical survival with Aza-based salvage protocols in similar patients treated at MDACC (Figure 3 – Part 1 and 2).

Grade 3/4 and Grade 2 immune mediated toxicities were observed in N=7 (14%) and N=6 (12%) patients, respectively. These included 8 episodes of pneumonitis, 2 nephritis, 2 transaminitis, and 1 skin rash. In almost all cases the toxicities responded rapidly to steroids, and 12 of the 13 patients were successfully rechallenged with nivolumab without recurrence of immune toxicities. One patient has come off study due to immune

toxicity (pneumonitis). Baseline and end of cycle 1 bone marrow was evaluated on 25 of the 35 evaluable patients, including 6 responders (CR/CRi/HI) and 19 non-responders. Patients who achieved a CR/CRi/HI had a baseline higher live total CD3 ($P=0.10$), CD8⁺ T-cells ($P=0.02$), and lower live CD4⁺Foxp3⁺PD1⁺ T-regulatory (T-reg) cells ($P=0.01$) infiltrate in the bone marrow suggesting potential biomarkers of response. On further evaluation of post cycle 1 and post cycle 2 BM the responders demonstrate a progressive increase in the live CD3⁺ and CD8⁺ BM infiltrate and an increase in CD8⁺ ICOS⁺ activated phenotype cells. On the other hand non-responders did not have an increase in the live CD3⁺ or T-cell subsets.

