Flow-cytometry (MFC) was performed on pre- and post-therapy BMAs, after 2 doses (end of cycle 1 or EOC1) and 4 doses (EOC2) of nivolumab in 19 of 23 responders (R) (CR/CRI/PR/HI) (83%) and 28 of 41 NRs (68%). 36 parameter CyTOF was performed at same time-points in 5 responders and 5 non-responders. On pretherapy BMAs, responders had a higher frequency of CD3⁺ ($p=0.04$) and CD8⁺ cells ($p=0.09$) on MFC. CD3⁺ in the pretherapy BMA with a cut-off of 13.2%, had a sensitivity of 74% and a specificity of 65% for predicting response. CD3⁺ was $>13.2\%$ in 26 of 47 patients (55%) who had an evaluable pretherapy BMA. Immunohistochemistry confirmed that CD3⁺ cells were increased in pretherapy BMs in responders. PhenoGraph clustering of all CD3-gated cells revealed 24 meta-clusters. The frequency of an effector CD8⁺ T cell cluster (C2) expressing CD45RA⁺PD1^{lo}Tbet^{hi}Eomes^{lo} was significantly higher in the pretherapy BMAs of responders versus non-responders (11.2% versus 2.5%; $p=0.002$), and was further expanded in responders but not in non-responders in the EOC1, EOC2, and EOC4 BMAs.

Figure 5A: Overall survival in patients with response/stable disease versus non-responders (N = 70)

[figure not shown]
[figure not shown]

Figure 5B. Overall survival among patients who were salvage 1 versus >salvage 1 at enrollment

2.6.3 Hypomethylating agents (HMAs) in combination with GO in AML:

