2.6.5 Rationale for protocol amendment and proposed changes

Given the emerging preclinical and clinical data outlined above, we propose an amendment to remove the 4-1BB mAb inhibitor arms and doublet arms containing IO only agents. We would instead like to add combinations that build on the doublets that have shown encouraging response rates and OS in R/R AML in recent years and have emerged as our priority regimens for patients with R/R AML, namely HMA+venetoclax and HMA+PD1/PDL1 antibody.

Specifically, we proposed the following changes:

- Removal of arms evaluating checkpoint modulating doublets: 1) OX40 mAb + avelumab, 2) OX40 mAb + azacitidine, 3) OX40 mAb + 4-1BB mAb, and 4) avelumab + 4-1BB mAb
- These arms will be replaced with arms built on a backbone of either HMA+venetoclax or HMA+avelumab: 1) azacitidine + venetoclax + GO, 2) azacitidine + avelumab + GO, and 3) azacitidine + venetoclax + avelumab

Previous arms that will be continued include: 1) OX40 mAb single-agent, which will confirm the safe dose of OX40 in AML for use in combination arms, 2) the triplet regimen of azacitidine + avelumab + OX40 mAb, and 3) GO + glasdegib.

The primary goal of this amendment is to shift to triplet regimens incorporating agents with established efficacy in AML (e.g. combination of azacitidine, GO and/or venetoclax) and to improve on commonly used doublets in RR AML such as HMA+venetoclax and HMA+PD1/PDL1 antibody.

2.7 Update as of 6/4/2019: amendment to open azacitidine + avelumab + OX40 mAb arm

To date, 4 patients have been treated with the OX40 mAb (PF-04518600) in this clinical trial. All patients were treated at the 0.3 mg/kg dose level. The number of cycles received prior to progression were 1 (n=2), 2 (n=1) and 3 (n=1). No DLTs, immune-related AEs or grade 3+ related AEs were observed. The following grade 3-5 AEs were observed all of which were attributed as unrelated to the OX40mAb: grade 3 confusion (n=1), grade 3 stroke (n=1), grade 4 sepsis (n=1), grade 4 hypotension (n=1), grade 4 ileus (n=4), grade 3 febrile neutropenic fever (n=3) and grade 5 multi-organ failure.

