Demographic/clinical characteristics and safety data will be summarized using descriptive statistics such as mean, standard deviation, median and range. The composite complete response (CRc) rates, partial response (PR), hematologic improvement (HI) rate, 4-week and 8-week mortality will be estimated along with the

95% credible intervals. Kaplan-Meier method will be used to estimate the relapse-free survival (RFS), morphologic leukemia free survival (MLFS), time to next therapy (TNT) and overall survival (OS). The two-sided log-rank tests will be used to assess the differences of time to events between groups. Cox proportional hazards regression model will be used to determine associations between MRD and OS.

All patients who received at least one dose of study drug will be included in the intent-to-treat analysis for efficacy and safety. We will follow standard reporting guidelines for adverse events. Safety data will be summarized by category, severity and frequency. Paired t-tests will be used to determine the immunological and molecular changes in the peripheral blood and bone marrow from baseline to the predefined time-points on-therapy.

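### The plan aims to relate immune changes to clinical response, but section 11 gives these markers only paired t-tests from baseline, which do not test that link and describe only patients who stay and give samples

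*Combined protocol and SAP*

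**What the plan says.** The rationale (section 2.4) sets out to understand AML immunology, "how that is changed by immune checkpoint therapies and non-immune checkpoint therapies, and how both of these are related to clinical response", and to develop predictive biomarkers. The exploratory objectives (section 1.3) include "To study immunological and molecular features at baseline and at predefined time-points on-therapy with each combination in the peripheral blood and bone marrow" and a gene-expression predictor of response.

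For these markers the statistical analysis plan in section 11.0 says: "Paired t-tests will be used to determine the immunological and molecular changes in the peripheral blood and bone marrow from baseline", followed by a reference to the predefined on-therapy time-points. Two other inferential methods are named, and neither concerns immune markers and response: "The two-sided log-rank tests will be used to assess the differences of time to events between groups" and "Cox proportional hazards regression model will be used to determine associations between MRD and OS". Section 7.2.13 mentions exploring mutations and cytogenetics against response. It names no method and does not extend this to immune markers.

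Section 7.2.13 makes all correlative samples optional and does not count missed ones as deviations. Sections 5.4.8 and 9.1.3 end treatment at clinically significant progression. Section 11.0 has no rule for missing marker samples and does not say how samples taken at progression enter the paired tests.

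**The concern.** A paired t-test of change from baseline asks whether the average change is zero among patients who have both samples. It does not ask whether change, or baseline level, differs between responders and non-responders. The stated goal therefore has no analysis behind it, although the sponsor made that comparison in its earlier azacitidine-nivolumab trial. Section 2.5 reports a progressive T-cell increase in responders and adds: "On the other hand non-responders did not have an increase in the live CD3".

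That report also shows why the mix of patients matters. If responders and non-responders change differently, and the chance of a later sample depends on response, the paired means at cycles 1, 2, 4 and 8 average over different mixes. A trend across them could be read as a growing drug effect when it partly reflects who is left.

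**Working it through.** **1. Is there a marker-response analysis?** The methods in section 11.0 sort as follows.
- CRc, PR, HI and early mortality: rates with credible intervals.
- RFS, MLFS, TNT and OS: Kaplan-Meier and log-rank, with the groups not defined.
- MRD and OS: Cox model.
- Immune and molecular change: paired t-tests.

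None compares an immune marker, or its change, by response. The documents give no sample size, power or error rate for the immune analyses, so there is no figure of the plan's own to reproduce.

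**2. What can one paired test show?** It estimates the mean of dᵢ = laterᵢ − baselineᵢ over patients with both samples, so min(dᵢ) ≤ mean ≤ max(dᵢ). A rise from baseline that no patient had is impossible. A simulation confirms this. It used 4,000 trials per setting, n = 24 or 30, 30% or 45% response, baseline means of 11.2 and 2.5 from section 2.6.2, assumed SDs of 2 between and within patients, and assumed retention of 90% of responders and 30% of non-responders. With no true change, the paired mean was −0.02 to 0.02 and rejection at two-sided 0.05 was 4.4% to 5.1%.

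**3. What can selection do?** It can overweight one group's change. Take 30% responders (the historical CRc rate in section 11.0), a change of 3 in responders and 0 in non-responders, and the same 90%/30% retention. The responder share among pairs is 0.27/(0.27 + 0.21) = 0.5625. The paired mean is 3 × 0.5625 = 1.69, against 3 × 0.30 = 0.90 in all patients.

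**4. What can happen across time-points?** Suppose the change is +1 SD in every responder and 0 in every non-responder, the same at each time-point. Let a and b be the shares of responders and non-responders with a sample. Then the paired mean is 0.3a/(0.3a + 0.7b). All values of a and b here are assumed.

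| Case | Cycle 1 | Cycle 2 | Cycle 4 |
|---|---|---|---|
| Strong loss, a/b | 1.00/1.00 | 0.95/0.50 | 0.80/0.10 |
| Paired mean (SD) | 0.300 | 0.285/0.635 = 0.449 | 0.240/0.310 = 0.774 |
| Milder loss, a/b | 0.83/0.68 | 0.83/0.45 | 0.75/0.15 |
| Paired mean (SD) | 0.249/0.725 = 0.343 | 0.249/0.564 = 0.441 | 0.225/0.330 = 0.682 |

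From cycle 1 to cycle 4 the ratio is 0.774/0.300 = 2.6 or 0.682/0.343 = 2.0, with no patient changing after cycle 1.

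**5. What do the documents say about selection?**
- Section 2.6.2 reports flow cytometry in 19 of 23 responders (83%) and 28 of 41 non-responders (68%), and 19 + 28 = 47. The same section gives 47 as the number with an evaluable pre-therapy marrow. These figures therefore fit having a baseline sample and are not evidence of later-sample retention. The difference is also compatible with chance (Fisher p about 0.25).
- Section 2.5 gives the only count of baseline plus end-of-cycle-1 marrows by response: 6 responders and 19 non-responders among 35 evaluable patients, of whom 11 had CR/CRi/HI. That is 6/11 = 55% and 19/24 = 79%, the opposite direction (Fisher p about 0.23). Put into step 4, it gives 0.164/(0.164 + 0.554) = 0.23, below the 0.30 seen with full sampling.
- Section 2.7 reports that the four Arm A patients received 1, 1, 2 and 3 cycles before progression. None reached cycle 4, but this is a count of cycles in a closed arm and says nothing about samples by response.

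**The case against.** The strongest reply is that the planned test is paired. A reader might infer that early exit of non-responders can produce a rise that no patient had. For change from baseline that is wrong, as step 2 shows; the artefact belongs to unpaired averages over different patients at each visit. Only drift between successive paired means survives, and section 11.0 names no contrast of cycle 1 with cycle 4, so the 2- to 2.6-fold figures do not correspond to any planned result. They matter only if the series of means is read as a time course.

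A reader might also take 83% against 68% as proof that non-responders' later samples are lost, or conclude that arms with more early exits will show larger effects. The documents support neither. The first is a misreading of baseline availability. The second needs responders to change more and exits to be mainly non-responders; moreover, the arms are not randomised and no between-arm marker test is planned.

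Samples at progression are planned and aim at the patients who leave. They soften the loss, but they are optional, and marrow at progression is collected only if possible. Finally, these are exploratory correlatives with no role in stopping or in the primary endpoint, which limits the consequence. None of this supplies the missing marker-response analysis.

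**Conclusion.** The point holds in two parts. First, and directly from the text, section 2.4 sets a goal of relating immune features and their change to clinical response, and section 11.0 contains no analysis that does so. This rests on no assumption. Second, later paired means describe only patients who remain and give samples, so they need not be comparable across time-points. This follows from optional sampling and stopping at progression, provided that change and sampling both depend on response.

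The size of the second part is unknown. The drift from 0.30 to 0.77 SD (or 0.34 to 0.68) shows what is possible under assumed retention and is not an estimate for this trial. The one relevant paired count, from an earlier trial, points the other way at cycle 1. The change is worth making because it is cheap and gives a stated aim a method; the primary conclusions of the trial do not depend on it.

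**What to change.** Extend the paired t-test sentence in section 11.0 to specify, for each marker and arm:
- **Main contrast:** responders (CRc) against non-responders, on baseline level and on change from baseline to end of cycle 1, with a rule for patients who have no response assessment.
- **Model:** a linear mixed model using all samples, with time, response and time-by-response, where numbers allow.
- **Reporting:** the number of pairs by response at each time-point.
- **Later time-points:** cycles 4 and 8 descriptive only, compared with earlier ones only within patients who have both samples.
- **Progression samples:** a statement of how they enter.

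Paired t-tests may stay as within-group summaries.

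**Cost.** The change needs SAP wording and modest extra analysis, with no extra sample collection. One point needs reconciling: section 7.2.13 collects blood and marrow on day 28 of cycle 1, but its assay lists name baseline, end of cycles 2 and 4, and progression. It should confirm that cycle 1 samples are assayed; if they are not at present, that adds assay cost. Intervals will be wider in small groups. With 24 patients, 30% response and full sampling, there are 24 × 0.3 = 7.2 responders and 16.8 non-responders. At cycle 4 under the strong-loss assumption, only 16.8 × 0.10 = 1.7 non-responders remain, which is why later results should be descriptive. The model also assumes that missingness depends only on response and on observed values.
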